6 STUDY PROCEDURES

6.1 Schedule of Events

Activity	Phone Screen	Screening Visit	Baseline Visit/ BCG Vaccine 1	BCG Vaccine 2	Outcome Visit/ Early Termination	Check-In Phone
		<-28days	Day 1	Day 28 +14 days	Day 84 ±5 days	Day 98 ±5 days
Informed Consent		x				
Inclusion/Exclusion Review	x	x				
Demographics	x	x				
Create IBCID		x				
Medical History	x	x				
Concomitant Medication Review	x	x	x	x	x	x
Family History		x				
Vital Signs, Height, Weight ¹		x	x	x	x	
Physical & Neurological Exam		x				
Screening Lab Tests for Eligibility ²		x				
BCG Vaccination			x	x		
Vaccination Site Monitoring			x	x	x	
Fundoscopy					x	
Safety Lab Tests ³				x	x	
Blood Draw for Biomarkers ⁴			x	x	x	
COVID-19 Testing ⁵		x				
PT/INR		x			x	
Fasting Lumbar Puncture for Biomarkers ⁴			x		x	
MoCA and FAQ		x			x	
Cognitive/Behavioral Assessment ⁶			x		x	
Adverse Event Review		x	x	x	x	x

[1] Height and weight will be measured and recorded at the Screening visit only.

[2] Eligibility lab tests include CBC with diff, CMP, TSH, Folate, B12, HIV antibodies, serum immunoglobulins, ESR, CRP, QuantiFERON-TB Gold Test, urinalysis

[3] Safety lab tests include CBC with diff, CMP, CRP and ESR.

[4] Blood biomarkers will include PBMCs for PPD and amyloid-beta stimulation assay / flow cytometry, and serum for IIR and AD biomarkers. CSF biomarkers will be used for cytology, IIR and AD biomarkers tubes for monocyte levels of innate immunity.

[5] COVID-19 Testing includes SARS-CoV-2 PCR (nasal swab)

[6] Cognitive assessments will include RBANS, NPI-Q

6.2 Study Visits

6.2.1 Screening

6.2.1.1 Telephone Pre-Screening

Subjects will be screened over the phone by study staff to determine eligibility and to ensure that the subject is safe to undergo all study assessments. These procedures include:

- Obtain verbal pre-screening informed consent from subject
- Assess inclusion and exclusion criteria
- Collect brief demographics
- Obtain neurocognitive disease diagnosis history, family history, and medical history, including COVID-19 diagnosis and previous exposure risk
- Review and document concomitant medications and therapies

During this call, study procedures will be discussed in detail and the subject will be given an opportunity to ask questions about the study. All other study procedures will take place after signing an IRB-approved consent form in person.

6.2.1.2 Screening Visit

All subjects who pass a telephone pre-screening will be invited to MGH CNY for a study visit. If necessary, some of the following procedures may be performed virtually to minimize the length of the office visit. This screening visit will take approximately two hours. The following procedures will be performed at the visit:

- Obtain written informed consent from subject
- Review inclusion and exclusion criteria, medical history including COVID-19 history and demographics, concomitant medications and therapies
- Vital signs, height, and weight
- Perform a physical, including inspection for BCG scar on either deltoid
- Perform a neurological examination
- Perform nasal swab testing of SARS-CoV-2 PCR
- Urinalysis
- Phlebotomy for screening tests
 - CBC with differential
 - Comprehensive metabolic panel (CMP)
 - Thyroid stimulating hormone (TSH)
 - B12
 - Folate
 - HIV antibodies
 - Tuberculosis (QuantiFERON-TB Gold Test)
 - C-Reactive Protein (CRP)
 - Erythrocyte sedimentation rate (ESR)
 - Serum immunoglobins (IgA, IgG, IgM)
 - PT/INR
- MoCA (version 8.1)
- FAQ
- Assess and document adverse events (AEs) after subject signs ICF

6.2.1.3 Screen Failures

Any subject who signs consent will be considered enrolled in the study. If a subject fails screening, *at a minimum*, the following information should be captured and entered into the Electronic Data System (EDC).

- Inclusion/Exclusion Criteria
- Demographics
- Reason for screen failure

6.2.1.4 Re-screening

One re-screen is allowed ≥ 30 days after the initial screening. All screening procedures will be repeated at the re-screen visit.

6.2.2 Baseline Visit/BCG Vaccine 1 (Day 1)

All subjects who pass screening will return to MGH CNY for the Baseline visit. At this visit, all baseline clinical measures will be collected, and the first BCG vaccine injection will be administered. The Baseline visit will occur within 28 days of the Screening visit. If necessary, baseline measures may be collected up to 3 days before the Day 1 vaccination visit. The visit will take approximately three hours and will include:

- Vital signs
- Assess any changes to medical history, concomitant medications and/or adverse events
- Neurobehavioral assessments
 - RBANS
 - NPI-Q
- Phlebotomy for biomarker research
- Fasting lumbar puncture for biomarker research
- First BCG vaccine administration followed by 30 minutes of monitoring

6.2.3 BCG Vaccine 2 (Day 28 + 14 days)

Subjects will be asked to return to MGH CNY for a second BCG vaccination visit 28 (+ 14) days after the first vaccination. This visit will take approximately one hour and will include:

- Vital signs
- Assess any changes to medical history, concomitant medications and/or adverse events
- Phlebotomy for safety labs
- Phlebotomy for biomarker research
- Vaccine site monitoring
- Second BCG vaccine administered followed by 30 minutes of monitoring

6.2.4 Outcome Visit (Day 84 \pm 5 days)

Subjects will be asked to return to MGH CNY for the final in-person visit at Day 84 (± 5) days to assess study outcomes. This visit will take approximately three hours and will include:

- Vital signs
- Assess any changes to medical history, concomitant medications and/or adverse events
- Vaccine site monitoring

- Neurobehavioral assessments
 - FAQ
 - MoCA (version 8.1)
 - RBANS
 - NPI-Q
- Phlebotomy for safety labs
- Phlebotomy for biomarker research
- Point of care PT/INR testing for lumbar puncture safety
- Focused Exam: Fundoscopy
- Fasting lumbar puncture for biomarker research

6.2.5 Follow-up Phone Call (Day 98 ± 5 days)

All subjects who complete the Outcome visit will be called on Day 98 (± 5) days by the study coordinator or clinician to review changes to concomitant medications and/or adverse events.

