5.5 Early Termination Visit (ET)

Subjects who decide to withdraw from the study at any point after receiving the initial BCG immunization will be invited to come in for an Early Termination Visit.

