6.2.6 Early Termination Visit

If the subject withdraws from the study before completion of all study visits, they may be invited to return to MGH CNY for a final visit. This visit will take approximately 2 hours and will include the following measures:

- Vital signs
- Assess any changes to medical history, concomitant medications and/or adverse events
- Neurobehavioral assessments – RBANS, NPI-Q, FAQ, MoCA
- Phlebotomy for biomarker research
- Phlebotomy for safety lab testing
- PT/INR (if opting for lumbar puncture)
- Optional fasting lumbar puncture

The option to decline any of the early termination procedures or the entire visit will be given to all participants withdrawing from the study.

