6.3.5 Vaccination Site Monitoring

Prior to the first vaccination, both deltoids will be inspected to confirm there is no evidence of previous BCG vaccination and no obvious symptoms that would contraindicate vaccine injection. At the Day 28 visit, prior to the second injection, the vaccination site will be inspected for any signs of local infection. At the Day 84 visit and if indicated by subject-reported AEs, the site of vaccination on the arm will be examined and any visible reactivity will be recorded.

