9 RISKS AND DISCOMFORTS

9.1 BCG Vaccine Risks

The BCG injection is associated with minimal, brief discomfort. The following risks may also be associated with BCG vaccination per the manufacturer product insert.

Although BCG vaccination often causes local reactions, serious or long-term complications are rare. Reactions that can be expected after vaccination include moderate axillary or cervical lymphadenopathy and induration and subsequent pustule formation at the injection site; these reactions can persist for as long as 3 months after vaccination. The intensity and duration of the local reaction depends on the depth of penetration of the puncture device and individual variations in patients' tissue reactions. Slight tenderness at the puncture site may be encountered as well as some itching. The initial skin lesions usually appear within 10–14 days and consist of small red papules at the site. The papules reach maximum diameter (about 3 mm) after 4 to 6 weeks, after which they may scale and then slowly subside. More serious local reactions include ulceration at the vaccination site, regional suppurative lymphadenitis with draining sinuses, and caseous lesions or purulent draining at the puncture site. These manifestations might occur up to 5 months after vaccination and could persist for several weeks.

Acute, localized irritative toxicities of BCG may be accompanied by systemic manifestations, consistent with a “flu-like” syndrome. Systemic adverse effects of 1–2 days’ duration such as fever, anorexia, myalgia, and neuralgia, often reflect hypersensitivity reactions. However, symptoms such as fever of 103 °F or greater, or acute localized inflammation persisting longer than 2–3 days suggest active infections, and evaluation for serious infectious complication should be considered.

Rare adverse events (mostly suppurative adenopathy) have been reported in Europe and other locales, mostly in the setting of mistakenly subcutaneous, rather than intradermal vaccination. The frequency of more severe cutaneous reactions, such as an ulcer >1 cm, axillary adenopathy which may be suppurative, or other localized skin reactions, is approximately 0.02% for first vaccinations and 0.04% for second vaccinations. Suppurative adenopathy is not treated but observed.

An allergic reaction can occur including serious reactions such as shock or anaphylaxis. Although anaphylaxis is very rare, the subjects will be observed for an allergic reaction after BCG vaccination.

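### Cheap improvement, low expected yield: the last scheduled adverse event contact comes 51–75 days after dose 2 and 92–102 days after dose 1, short of the 5-month window in section 9.1; one later call would cover it

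*Combined protocol and SAP*

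**What the plan says.** Dose 1 is given on Day 1 (section 6.2.2). Section 6.2.3 places dose 2 "28 (+ 14) days after the first vaccination", shown as Day 28 + 14 days in the schedule (6.1). The final in-person visit is Day 84 ± 5 (6.2.4). Routine site inspection ends there: "At the Day 84 visit and if indicated by subject-reported AEs, the site of vaccination on the arm will be examined" (6.3.5). The last scheduled contact is a telephone review of medications and AEs (6.2.5): "All subjects who complete the Outcome visit will be called on Day 98", ± 5 days.

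Subjects who withdraw after dose 1 do not get that call. They "will be invited to come in for an Early Termination Visit" (5.5), and section 6.2.6 adds: "The option to decline any of the early termination procedures or the entire visit will be given to all participants".

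Section 9.1 introduces its risk list with "The following risks may also be associated with BCG vaccination per the manufacturer product insert". For the more serious local reactions (ulceration, suppurative lymphadenitis, purulent drainage) it states: "These manifestations might occur up to 5 months after vaccination and could persist for several weeks". For the commoner, expected lymphadenopathy and site reactions it allows persistence of up to 3 months. The frequency of more severe cutaneous reactions "is approximately 0.02% for first vaccinations and 0.04% for second vaccinations".

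AE monitoring ends when participation ends (11.3.1). Section 5.4.2 acknowledges that disseminated infection usually appears after the study's timeline. No section says the same of local reactions.

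**The concern.** The protocol states a period in which late local reactions might appear, and its own contact schedule stops before that period is over, for both doses. The second dose is followed for the shorter time, and section 9.1 gives it the higher quoted rate of severe cutaneous reactions.

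Safety and tolerability is a secondary objective (3.2), and the findings are meant to inform later placebo-controlled trials (8.1). Two things are at stake. A late reaction would come to light only if the subject reported it unprompted. In addition, the outcome of an AE still open at the call may never be recorded: section 11.3.3 asks for a resolution date and outcome, and section 11.3.5 allows an update to be entered, but no section requires staff to seek one after the last contact. Subjects who withdraw and decline the termination visit have no scheduled follow-up at all from that point.

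**Working it through.** The protocol gives no figure for length of follow-up after each dose, so there is none to reproduce. The check is calendar arithmetic on the visit windows.

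**Inputs.** Dose 1: Day 1 (6.2.2). Dose 2: Day 28–42 (6.1, 6.2.3). Last in-person visit: Day 79–89 (6.2.4). Last call: Day 93–103 (6.2.5). Window for the more serious local reactions: 5 months (9.1), taken as 5 × 30.4 = 152 days. Persistence of expected reactions: 3 months (9.1), 3 × 30.4 ≈ 91 days.

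**Dose to last call.**
- Dose 2: 93 − 42 = 51 to 103 − 28 = 75 days, or 7.3–10.7 weeks; nominally 98 − 28 = 70.
- Dose 1: 93 − 1 = 92 to 103 − 1 = 102 days.
- If dose 2 is counted as 28–42 elapsed days after Day 1 (Day 29–43), its range is 50–74 days. Nothing turns on the one-day difference.

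**Dose 2 to last routine site inspection.** 79 − 42 = 37 to 89 − 28 = 61 days.

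**Shortfall against 152 days.**
- Dose 2: 152 − 75 = 77 to 152 − 51 = 101 days.
- Dose 1: 152 − 102 = 50 to 152 − 92 = 60 days.

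**Shortfall against 91 days (expected reactions).** Dose 1 is just covered (92–102). Dose 2 is not (51–75).

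**Expected yield**, at 0.02% for dose 1 and 0.04% for dose 2, assuming these rates span the whole risk period (the documents state no period):
- 20 participants (3.1): 20 × (0.0002 + 0.0004) = 0.012 events. Chance of at least one: 1 − (0.9998 × 0.9996)^20 ≈ 1.2%.
- 12 participants (the number in 7.4 and 8.1): 12 × 0.0006 = 0.0072 events; chance about 0.7%.
- The share falling after the last call is unknown. It lies between zero and these values.

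**When a later call would have to fall.** After two doses: 28 + 152 = Day 180 to 42 + 152 = Day 194. After one dose: 1 + 152 = Day 153.

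**Reach for disseminated infection** (4 months to 2 years, taken as days 122–730, a span of 608 days). A call 152 days after dose 2 covers 152 − 122 = 30 of these days. The same call is 179–193 days after dose 1 and covers 57–71 of them.

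**The case against.** The strongest reply is that this is a preference about follow-up length in a small exploratory pilot. The primary objective is biomarker selection, section 8.1 attaches no claims to any outcome, and the calls will probably find few or no events. The only time course in section 9.1, for the initial skin lesions, has onset at 10–14 days and maximum size at 4–6 weeks. The current last contact falls after that peak for both doses. All of this stands, and it is why the point is an improvement and not an error.

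Three stronger readings are tempting, and the documents do not support them.
- A reader might infer that the protocol expects serious late reactions. It says only that they might occur, and it calls serious or long-term complications rare. What it does expect is the milder lymphadenopathy and site reactions.
- A reader might take 51–75 days out of 152 to mean that half or more of the dose 2 risk goes unobserved. These are elapsed days. The documents give no distribution of onset times.
- A reader might treat the quoted percentages as an upper limit on missed events. Their observation period is not stated, and their case definition differs somewhat from the list tied to the 5-month window.

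Short follow-up of early terminators also partly respects their choice to stop. Any later contact needs their agreement when they withdraw.

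The objection does not remove the mismatch itself. The 5-month period is the protocol's own, no later contact is scheduled, and the acknowledged time limit covers disseminated infection only. Nor does the low event rate answer the point on resolution: expected lymphadenopathy after dose 2 can outlast the last contact, and the exclusion of the normal scab-and-scar reaction from AE reporting (11.3.1) does not mention lymph nodes.

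**Conclusion.** The point holds as a cheap improvement with low expected yield. Scheduled AE follow-up stops 77–101 days short of the stated window after dose 2 and 50–60 days short after dose 1. After dose 2 it also stops short of the 3 months for which expected reactions can persist. Acute reactions, and those appearing within about 7 weeks of dose 2, are covered for subjects who complete the Outcome visit and take the call.

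No conclusion of the trial is invalidated. The gain is coverage of the stated window and a recorded outcome for open AEs, not an estimate of a rate. The result rests on months of 30.4 days, on day counts accurate to within one day, and, for the yield only, on the assumption that the quoted rates span the whole risk period.

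**What to change.** Add to sections 6.1 and 6.2.5 one telephone AE contact at 5 months after the last dose received: about Day 180–194 after two doses, Day 153 after one. Give it a stated window, such as +14 days. Offer it to everyone who received any dose, including early terminators who agree to it at withdrawal. Ask about ulceration, drainage, swollen lymph nodes, persistent fever, night sweats and weight loss, and examine the site if the answers call for it. In section 11.3, keep AE collection open until this call and record the outcome of any AE that was open at the Day 98 call.

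**Cost.** A protocol and consent amendment, about 20 short calls (12 if the number in 7.4 and 8.1 applies) and occasional unscheduled site examinations. For two-dose subjects the last contact moves from 180 − 103 = 77 to 194 − 93 = 101 days later, about 3 months, plus any part of the call window that is used. Biomarker and cognitive analyses rest on data to Day 84 and need not wait. The call would add little for disseminated infection, as the 30 (dose 2) and 57–71 (dose 1) of 608 days show.

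**If the call is not added**, state beside the safety results that they cover about 7–11 weeks after dose 2. That costs only wording.

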6.2.6 Early Termination Visit

If the subject withdraws from the study before completion of all study visits, they may be invited to return to MGH CNY for a final visit. This visit will take approximately 2 hours and will include the following measures:

- Vital signs
- Assess any changes to medical history, concomitant medications and/or adverse events
- Neurobehavioral assessments – RBANS, NPI-Q, FAQ, MoCA
- Phlebotomy for biomarker research
- Phlebotomy for safety lab testing
- PT/INR (if opting for lumbar puncture)
- Optional fasting lumbar puncture

The option to decline any of the early termination procedures or the entire visit will be given to all participants withdrawing from the study.

6.2.7 Protocol Deviations

A protocol deviation is any noncompliance with the current clinical trial protocol. The noncompliance may be on the part of the subject, the PI or Co-Is, or the study staff. As a result of deviations, corrective actions will be developed by the PI or Co-Is and implemented promptly. All deviations from the protocol must be addressed in the subject's documents. Protocol deviations will be sent to the IRB per their guidelines and entered in the Protocol Deviations Log in the EDC System.

6.2.8 Missed Visits and Procedures

Missed visits and any procedures not performed (not attempted) for reasons other than illness, injury, or progressive disability (i.e.: a subject is physically unable to perform them) will be reported as protocol deviations.

Procedures or visits not performed due to illness, injury, or disability, including procedures that were attempted but failed (i.e.: blood samples unable to be drawn after multiple attempts or weight unable to be obtained due to subject immobility) will not be reported as protocol deviations.

6.3 Clinical Assessments

Assessments will be performed at designated time-points throughout the study for clinical evaluation. In addition to the assessments evaluated below, subjects will provide information on their demographics, past medical and AD history, family history, and medication usage.

Subject interviews and the neurocognitive and neuropsychiatric assessments detailed below may be conducted virtually using Zoom videoconferencing platform depending on institutional guidance relating to the COVID-19 pandemic and subject consent. Any visit components conducted virtually will be documented as such and efforts will be made to collect all intrasubject clinical assessments in the same format (virtually or in person).

6.3.1 Safety Measures

6.3.1.1 Vital Signs, Height, Weight

Vital signs, including systolic and diastolic blood pressure, pulse rate (radial artery)/minute, respiratory rate/minute, and temperature will be assessed at the Screening, Baseline, Day 28, and Day 84 visits. Verbal weight may be documented for those subjects utilizing a wheelchair. Height and weight will be measured and recorded at the Screening visit only.

6.3.1.2 Clinical Laboratory Assessments

Study participants will be asked to provide approximately 25 mL of blood for eligibility and safety lab analysis at the Screening visit, 11 mL for safety lab analysis at Day 28, and 12 mL for safety lab analysis at Day 84, for a total of 48 ml (3.3 tablespoons) throughout the study. The participant will have his or her whole blood collected by either a nurse or phlebotomist from a peripheral vein. Blood will be handled, processed, and analyzed in accordance with regulations set forth by the American Society for Clinical Pathology and the College of American Pathologists.

Safety Laboratory Tests

Lab test	Source	Volume required [mL] (total)	Completed at following visits
Coagulation Testing (PT/INR)	Finger prick or intravenously from peripheral vein	1 (2)	Screening, Day 84
Complete Blood Count with Differential Testing		3 (9)	Screening, Day 28, Day 84
Complete Metabolic Panel Testing		5 (15)	Screening, Day 28, Day 84
C-Reactive Protein Testing (CRP)		1 (3)	Screening, Day 28, Day 84
Erythrocyte Sedimentation Rate (ESR)		2 (6)	Screening, Day 28, Day 84
HIV Antibody Testing		6 (6)	Screening
QuantiFERON-TB Gold Test		4 (4)	Screening
Serum Folate / B12 Testing		1 (1)	Screening
Serum Immunoglobins		1 (1)	Screening
Serum Thyroid Stimulating Hormone Testing		1 (1)	Screening
Urinalysis	Urine cup	10 (urine)	Screening
SARS-CoV-2 PCR	Nasal swab	n/a	Screening

All subjects will have safety laboratory tests at the designated visits outlined in the protocol. These samples will be analyzed at a central laboratory. The SI may order additional testing, if thought to be necessary, to further assess an adverse event (AE), or if there is any suspicion that a subject may be pregnant, throughout the course of the study.

Tests for Complete Blood Count (CBC) and Prothrombin Time and International Normalized Ratio (PT/INR) which are required prior to performing a lumbar puncture may be performed using CLIA waived point of care testing using the Sysmex XW-100 CBC analyzer and the Roche CoaguChek XS Plus PT/INR analyzer.

6.3.2 Physical and Neurological Examination

A physical and neurological examination will be performed at the Screening visit. The following systems will be examined: general appearance, head, eyes, ears, nose, throat, neck, chest, heart, abdomen, extremities, edema, peripheral vascular, skin and appendages, musculoskeletal, central nervous system and back.

A focused fundoscopy examination will be repeated at the outcome visit for assessment of increased intracranial pressure.

